4 INTRODUCTION

4.1 Background

Tetra Discovery Partners, Inc. is a central nervous system (CNS) biotechnology company that uses structure-based drug design to discover negative allosteric modulators (NAMs) of phosphodiesterase-4 (PDE4) subtypes for neurological and psychiatric diseases.

Tetra has developed a mechanistically novel class of drugs to address cognitive impairment across multiple psychiatric and neurological indications. These new drugs selectively target subtypes of phosphodiesterase type-4D (PDE4D).^{3,4} The PDE4D enzyme subtype is a highly validated CNS target for improving cognition.

4.2 Rationale

Fragile X syndrome (FXS) is a disorder in which affected individuals display intellectual disability as well as symptoms typical of autism spectrum disorder, due to silencing of the X-linked, fragile-X mental retardation-1 (*FMR1*) gene. Dysregulation of cAMP metabolism is a consistent finding in patients and in preclinical models of FXS. BPN14770, a prototypic phosphodiesterase-4D negative allosteric modulator (PDE4D-NAM) Daily treatment of adult male *fmr1* C57Bl6 knock-out mice with BPN14770 for 14 days reduced hyperarousal, improved social interaction, and improved natural behaviors such as nesting and marble burying as well as dendritic spine morphology. There was no decrement in behavioral scores in control mice treated with BPN14770. The behavioral benefit of BPN14770 persisted two weeks after washout of the drug. Thus, BPN14770 may be useful for the treatment of FXS with potential expansion to the treatment of autism spectrum disorder.⁵

A total of 136 subjects have received BPN14770 either as a single dose or as a multiple dose regimen. Of these subjects, 106 (78%) were \leq 55 years of age and 30 (22%) were \geq 60 years of age.

The single dose escalation study (-101) in 24 subjects ≤ 55 years of age determined that a single 100mg dose was the maximum tolerated dose of BPN14770, based on the occurrence of nausea and vomiting in the majority of subjects at this dose. There were no notable adverse events in other body systems, no observed changes in vital signs or electrocardiogram, no adverse laboratory findings, and no serious adverse events were recorded. The multiple dose escalation study assessed 15 mg, 30 mg, and 50 mg doses given BID to 18 subjects ≤45 years of age and doses of 10 mg, 20 mg, and 40 mg given BID to 30 subjects ≥ 60 years of age. All of these doses were well tolerated. An additional cohort of 6 subjects ≤45 years of age received 75mg once daily in order to compare the safety and PK profiles to the 100mg MTD determined in the single dose study. The 75 mg dose was associated with GI adverse experiences, confirming the findings at 100 mg in the single ascending dose study. The BPN14770 doses assessed in the scopolamine challenge study were 10 mg and 50 mg QD. Of the 38 subjects enrolled, 37 received at least one of the two doses of BPN14770; one subject withdrew from the crossover study prior to a dosing cohort containing BPN14770.

Protocol: BPN14770-CNS-203 Tetra Discovery Partners, Inc.
Date: 25 June 2018 Confidential

In the multiple ascending dose study (-102), BPN14770 administered twice daily to healthy elderly subjects was associated with improvement in complex attention/working memory, delayed recall of verbal information, and delayed recall of visual information (10 and 20 mg doses). No beneficial or detrimental effects were observed on other cognitive tasks studied. The 40-mg BID dose was not associated with improvement in any cognitive domain, possibly because of a higher frequency of adverse events, primarily headaches, at this dose level. Therefore, a daily dose of 25 mg bid was chosen for this clinical study in FXS.

4.3 Risk/Benefit

4.3.1 Preclinical Pharmacology

BPN14770 is a first-in-class, subtype selective, phosphodiesterase type-4D-negative allosteric modulator (PDE4D-NAM). The unique mechanism of action and subtype selectivity distinguishes BPN14770 from the two approved PDE4 inhibitors, roflumilast (DalirespTM) and apremilast (OtezlaTM). BPN14770 does not bind to the active site of the PDE4 enzyme and, unlike roflumilast and apremilast, does not cause emesis in ferrets, cynomolgous monkeys or marmosets; furthermore, it has not been found to cause mesenteric vasculopathy in rats or dogs in toxicological studies of 3 months duration. Thus, BPN14770 presents a unique procognitive and preclinical safety profile.

Clearance of BPN14770 by hepatocytes from human, rat, dog and monkey, expressed as hepatic extraction ratio (EH), was 16%, 8.2%, 17%, and 12%, respectively. Qualitative metabolite profiling in human, rat, dog, and monkey hepatocytes showed a single metabolite in human (<1% parent). BPN14770 was highly bound to plasma proteins in all species tested. The fraction unbound (free) was 0.5, 0.4, 0.2, and 0.5%, for mouse, rat, dog, and human, respectively.

BPN14770 is highly bioavailable in rats, mice and dogs (F% = 100), distributes to brain (B/P = 0.32-0.48), and has a plasma $t_{\frac{1}{2}}$ of 4.8 hours in rats, 10.9 hours in mice, and 11 hours in dogs. The multi-species pharmacokinetic data suggest that BPN14770 will have adequate half-life for once daily oral administration in humans. In bile duct cannulated rats, BPN14770 was eliminated as a conjugate through the bile. Only the unchanged drug was detected in plasma, and no BPN14770 was detected in urine.

BPN14770 did not affect cardiovascular function in beagle dogs at doses up to 100 mg/kg, nor did the compound affect respiratory function or exert neuropharmacologic effects in rats at doses up to 60 mg/kg. In the in vitro human Ether-à-go-go-Related Gene (hERG) assay, an increase in current of 12% and 33% was seen at concentrations of 10 and 30 μ M, respectively. No IC₅₀ could be calculated due to this minor increase in current.

In rat toxicology studies of 28-days and 13-weeks, BPN14770 was well tolerated up to 60 mg/kg with no deaths on study, and no adverse hematology, clinical chemistry, liver weight or gross necropsy findings. There were no microscopic findings. Unlike the PDE4 inhibitors roflumilast and apremilast, BPN14770 did not cause mesenteric vasculopathy at the doses studied.

In dog toxicology studies of 28-days and 13-weeks, the no observed adverse effect level (NOAEL) for BPN14770 was 30 mg/kg. At 100 mg/kg in the 28-day study, BPN14770 caused inappetance and weight loss and in female dogs an approximately 30 msec increase in QTc with a concomitant increase in heart rate of 10 bpm. There were no changes in hematology or ophthalmology. Macroscopic observations included pale livers in two of eight animals at 100

mg/kg which correlated with mild alanine transaminase (ALT) elevation only in those two animals. Microscopic changes of periportal hepatocellular cytoplasmic vacuolation were observed in the livers of one male and two female dogs at 100 mg/kg. No liver changes were observed in recovery dogs suggesting that these changes, if present, were reversible.

4.3.2 Clinical Experience

4.3.2.1 BPN14770-CNS-101

A first-in-human (FIH), single ascending dose (SAD) trial (BPN14770-CNS-101) in 24 healthy subjects at doses ranging from 5 mg to 100 mg has been completed. The results from this study indicate single doses of BPN14770, in the range of 5 mg to 100 mg, were safe and generally well tolerated. The maximum tolerated dose (MTD) was determined to be 100 mg, after 4 of 6 subjects in this dose group experienced nausea and, of those, two experienced vomiting.

The most commonly reported treatment-emergent, drug-related adverse events were nausea and vomiting. No safety signals were noted in the results of the other safety analyses. No deaths or other serious adverse events were reported. No subjects withdrew from the study due to adverse events.

In the SAD trial, detectable plasma BPN14770 concentrations were measured after dosing (at all 4 dose levels) starting between 0.5 hour and 1 hour after dosing, continuing through at least 48 hours after dosing. Drug absorption was variable but moderately rapid with median time to maximum concentration (T_{max}) values ranging from 1.5 to 3 hours. The plasma pharmacokinetics of BPN14770 after oral administration appeared to be linear for single doses ranging from 5 to 100 mg; although a slight trend for a greater than proportional increase in exposure was observed in the 100-mg group as compared to the lower dose groups. The apparent terminal elimination half-life of BPN14770 was consistent among dose groups and averaged between 11 and 13 hours. Based on the preclinical models, the concentrations associated with doses as low as 15 mg were potentially adequate to produce cognitive improvement after once- or twice- per day dosing.

4.3.2.2 BPN14770-CNS-102

In the multiple ascending dose (MAD) trial (BPN14770-CNS-102), 76 healthy young and elderly subjects were administered multiple doses of BPN14770 twice daily (every 12 hours) for 8 days. Young subjects (≤45 years; n=18 treated, 7 placebo) received twice-daily doses of 15 mg, 30 mg, 50 mg or placebo for 8 days. Elderly subjects (≥60 years; n=30 treated, 15 placebo) received twice-daily doses of 10 mg, 20 mg, and 40 mg for 8 days. Twice-daily dosing was selected to ensure adequate BPN14770 levels in the brain and plasma throughout the day and night. An additional cohort of 6 young subjects received a once-daily dose of 75 mg for 8 days to obtain additional safety and pharmacokinetic (PK) data at a dose level close to the MTD determined in the SAD study.

No deaths or serious adverse events were reported, and no subjects in either the young or elderly cohorts withdrew from the study due to adverse events. All treatment-emergent adverse events resolved without sequelae by the follow-up visit.

Protocol: BPN14770-CNS-203 Tetra Discovery Partners, Inc.
Date: 25 June 2018 Confidential

All study-drug related adverse events that occurred in more than 1 young subject were in the 75-mg QD dose group and consisted of nausea (reported by 4 of 6 subjects, vomiting (reported by 2 of 6 subjects who also experienced nausea), and decreased appetite (reported by 3 of 6 subjects). Across the young subject cohorts, all but 2 of the reported adverse events were mild in severity; moderate nausea and vomiting were reported in 1 of 6 subjects (16.7%) in the 75-mg QD dose group on Day 2 of multiple dosing. These events were considered by the Investigator as probably related to study treatment, resolved without sequelae within 13 hours of onset, and did not recur upon subsequent dosing. Among the young subject dose groups, no clinically significant effects of multiple oral doses of BPN14770 (15 mg, 30 mg, 50 mg, or 75 mg) were observed on biochemistry, hematology, or urinalysis; vital signs; or ECGs.

Among the elderly subject cohorts, the percentage of subjects who experienced at least one treatment-emergent adverse event was similar between the 10-mg BID, 20-mg BID, and placebo groups (ranging from 30% to 50%) and was higher for the 40-mg BID dose group (90%). Adverse events reported in 2 or more elderly subjects within a dose group were all reported by subjects in the 40-mg dose group and consisted of diarrhea, increased alanine and aspartate aminotransferase, hot flush (each reported at a frequency rate of 20%) and headache (reported at a frequency rate of 40%). Among the elderly subject dose groups, no clinically significant effects of multiple oral doses of BPN14770 (10 mg, 20 mg, or 40 mg) were observed on biochemistry, hematology, or urinalysis; vital signs; or ECGs.

With respect to cognitive testing, BPN14770 10 mg given twice daily was associated with improvement in complex attention/working memory and delayed recall of both visual and verbal information. Treatment with BPN14770 20 mg twice daily was associated with similar benefits as the 10 mg twice daily regimen, excluding improvement in delayed recall of visual information. Neither the 10- or 20-mg BID regimens was associated with improvement in psychomotor function, visual, or verbal learning, or executive function. The 40-mg BID regimen was not associated with improvement in any cognitive domain.

Pharmacokinetic analyses found that steady-state appeared to be reached after 3 to 4 days of BID or QD dosing in both young and elderly subjects. Following BID dosing of BPN14770 in healthy young subjects, Cmax and AUC12 appeared to increase in a greater than dose-proportional fashion from 15 mg to either 30 mg or 50 mg. A moderate degree of accumulation (up to approximately 5-fold) was observed after BID dosing in healthy young subjects, with less accumulation (approximately 2-fold) after QD dosing.

In healthy young subjects, mean peak to trough fluctuation was similar among BID regimens, ranging from 171% to 179%, and was 337% for the QD regimen. In healthy elderly subjects, mean peak to trough fluctuation was similar among BID regimens, ranging from 156% to 249%.

4.3.2.3 BPN14770-CNS-103

The third Phase 1 trial of BPN14770 (BPN14770-CNS-103) was a randomized, double-blind, placebo-controlled, 6-period crossover study to evaluate the effects of BPN14770 10 and 50 mg in reversing scopolamine-induced cognitive impairment in healthy volunteers. A positive control, donepezil 10 mg, was included, and additivity of BPN14770 50 mg to donepezil 10 mg in

Protocol: BPN14770-CNS-203 Tetra Discovery Partners, Inc.

Date: 25 June 2018 Confidential

reversing scopolamine effects was also evaluated. A total of 38 subjects were enrolled into the study.

The Cogstate Computerized Battery Test results suggest that, as expected, a 0.5 mg dose of scopolamine induced a decline in cognitive function, while a 10-mg dose of donepezil ameliorated this decline. Doses of 10 or 50 mg of BPN14770 did not produce a systematic reversal of the scopolamine-induced cognitive decline, administered alone or with a 10-mg dose of donepezil.

BPN14770 was safe and generally well tolerated when administered with scopolamine in healthy subjects. The incidence of nausea and vomiting increased several fold when either BPN14770 50 mg or donepezil was administered with scopolamine, or when both BPN14770 and donepezil were administered with scopolamine, compared to BPN14770 10 mg, placebo, or scopolamine alone.

4.4 Study Objectives and Endpoints

4.4.1 Study Objectives

In male Fragile X patients aged 18-45 years, inclusive, receiving standard medications:

- To obtain a preliminary assessment of the efficacy of BPN14770 25 mg bid
- To evaluate the safety and tolerability of BPN14770 25 mg
- To obtain pharmacokinetic, pharmacodynamic, and biomarker data on BPN14770

4.4.2 Exploratory Efficacy Outcome Measures

The following instruments will be used to assess the exploratory efficacy endpoints:

- NIH Toolbox Cognitive Battery Modified for Intellectual Disabilities (NIH-TCB)
- Test of Attentional Performance (KiTAP)
- Clinical Global Impression Severity Investigator rated (CGI-S)
- Clinical Global Impression Improvement Investigator rated (CGI-I)
- VAS Rating Scale using patient-specific behavioral anchors
- Aberrant Behavior Checklist (ABC)
- Anxiety, Depression, and Mood Scale (ADAMS)
- Vineland-3 Rating Scale
- Event-Related Potentials (ERP)
- Eye Tracking

4.4.3 Safety and Tolerability Endpoints

The following safety assessments will be conducted during the study.

- Treatment-emergent Adverse events
- Changes in vital signs
- Clinical laboratory evaluations (chemistry, hematology, urinalysis)
- Changes in electrocardiogram (ECG) measurements

4.4.4 Pharmacokinetic Endpoints

Plasma BPN14770 concentrations will be measured to verify that study drug is present when expected and to estimate plasma exposure after 12 weeks of treatment.

4.4.5 Biomarkers

Retained plasma samples may be used to explore biomarkers potentially associated with FXS.

5 INVESTIGATIONAL PLAN

5.1 Overall Study Design

This is a single center, Phase 2, randomized, double-blind, placebo-controlled, 2-period crossover study to obtain preliminary assessment of the effects of BPN14770 in patients with Fragile X Syndrome. As schematic display of the study design is shown in Figure 1.

[figure not shown]
The study will consist of a Screening period of up to 28 days prior to initial study drug administration, followed by two 12-week double-blind treatment periods. The screening and baseline visits may occur at the same time, provided the results of safety labs can be obtained. No washout period will be utilized between double-blind treatment periods; instead, efficacy and biomarker assessments during the second double-blind period (Period 2) will be obtained after a minimum of 6 weeks to allow for drug washout. A final follow-up phone contact for safety is planned one week after the conclusion of Period 2.

Eligible patients will be randomized in a blinded, balanced (1:1) fashion to receive either BPN14770 25mg bid or matching placebo during Period 1, followed by the opposite treatment during Period 2.

Brief cognitive and behavioral assessments will be performed during each clinic visit. Safety and tolerability assessments throughout the study will include adverse event monitoring, ECGs, vital signs, blood chemistry, hematology, and urinalysis.

Pharmacokinetic samples will be collected at screening and at end of Periods 1 and 2 (Week 12to confirm that study drug is present when expected and to estimate plasma exposure.). Biomarker samples will be collected at the time the pharmacokinetics samples are obtained.

Figure 1 Study Design Schematic

5.1.1 Dose Selection

The dose of 25 mg BPN14770 to be taken twice daily was chosen for testing in this study.

Based on pharmacokinetic data from study BPN14770-CNS-102 (MAD), average plasma concentrations of BPH14770 at 10 mg dosing are projected to be approximately 60 ng/ml. Therefore, the lower dose of 10 mg has the potential to demonstrate efficacy in this study, although given the uncertainties of translation from preclinical models, it may be below the effective range. On the other hand, the 25 mg dose should be above that needed for efficacy, with projected average plasma concentrations over 200 ng/ml. The twice-daily dose of 25mg selected for this study falls well within the tolerance limits defined by the SAD and MAD studies, as noted above.

5.2 Study Duration

The total duration of the study for each subject will be up to 29 weeks, including a maximum of a 4-week screening period, two 12-week double-blind Treatment Periods, and a follow-up call approximately 1 week after last treatment.

6 SELECTION AND WITHDRAWAL OF SUBJECTS

6.1 Study Population

Individuals are eligible for the study if they meet all of the inclusion and none of the exclusion criteria. The criteria below will be assessed at the Screening visit which should within 28 days prior to first study drug administration. The Screening and Baseline Visits may be combined if site procedures allow.

6.2 Subject Inclusion Criteria

1. Subject is male aged 18 to 45 years, inclusive.

Protocol: BPN14770-CNS-203 Tetra Discovery Partners, Inc.
Date: 25 June 2018 Confidential

2. Subject has Fragile X Syndrome with a molecular genetic confirmation of the full Fragile X Mental Retardation (FMR1) mutation (≥200 CGG repetitions).

- 3. Current treatment with no more than 3 prescribed psychotropic medications. Anti-epileptic medications are permitted and are not counted as psychotropic medications if they are used for treatment of seizures. Anti-epileptics for other indications, such as the treatment of mood disorders, count towards the limit of permitted medications.
- 4. Permitted concomitant psychotropic medications must be at a stable dose and dosing regimen for at least 2 weeks prior to Screening and must remain stable during the period between Screening and the commencement of study medication.
- 5. Anti-epileptic medications must be at a stable dose and dosing regimen for 12 weeks prior to Screening and must remain stable during the period between Screening and the commencement of study medication.
- 6. Subjects with a history of seizure disorder who are currently receiving treatment with anti-epileptics must have been seizure-free for 3 months preceding Screening, or must be seizure-free for 3 years if not currently receiving anti-epileptics.
- 7. Behavioral and therapy treatments/interventions must be stable for 4 weeks prior to Screening and must remain stable during the period between Screening and the commencement of study medication, and throughout the study. Minor changes in hours or times of therapy that are not considered clinically significant will not be exclusionary. Changes in therapies provided through a school program, due to school vacations, are allowed.
- 8. Subject must be willing to practice barrier methods of contraception while on study, if sexually active. Abstinence is also considered a reasonable form of birth control in this study population.
- 9. Subject has a parent, legal authorized guardian or consistent caregiver.
- 10. Subject and caregiver are able to attend the clinic regularly and reliably.
- 11. Subject is able to swallow tablets and capsules.
- 12. For subjects who are not their own legal guardian, subject's parent/legal authorized guardian is able to understand and sign an informed consent form to participate in the study.
- 13. If subject is his/her own legal guardian, he/she can understand and sign informed consent to participate in the study.
- 14. If subject is not their own legal guardian, the subject provides assent for participation in the study, if the subject has the cognitive ability to provide assent.

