Study Phase:	Phase 2

least 2 weeks prior to Screening and must remain stable during the period between Screening and the commencement of study medication.

- 5. Anti-epileptic medications must be at a stable dose and dosing regimen for 12 weeks prior to Screening and must remain stable during the period between Screening and the commencement of study medication.
- 6. Subjects with a history of seizure disorder who are currently receiving treatment with anti-epileptics must have been seizure-free for 3 months preceding Screening, or must be seizure-free for 3 years if not currently receiving anti-epileptics.
- 7. Behavioral and therapy treatments/interventions must be stable for 4 weeks prior to Screening and must remain stable during the period between Screening and the commencement of study medication, and throughout the study. Minor changes in hours or times of therapy that are not considered clinically significant will not be exclusionary. Changes in therapies provided through a school program, due to school vacations, are allowed.
- 8. Subject must be willing to practice barrier methods of contraception while on study, if sexually active. Abstinence is also considered a reasonable form of birth control in this study population.
- 9. Subject has a parent, legal authorized guardian or consistent caregiver.
- 10. Subject and caregiver are able to attend the clinic regularly and reliably.
- 11. Subject is able to swallow tablets and capsules.
- 12. For subjects who are not their own legal guardian, subject's parent/legal authorized guardian is able to understand and sign an informed consent form to participate in the study.
- 13. If subject is his/her own legal guardian, he/she can understand and sign informed consent to participate in the study.
- 14. If subject is not their own legal guardian, the subject provides assent for participation in the study, if the subject has the cognitive ability to provide assent.

Subject Exclusion Criteria

- 1. History of, or current cardiovascular, renal, hepatic, respiratory, gastrointestinal, psychiatric, neurologic, cerebrovascular, or other systemic disease that would place the subject at risk or potentially interfere with the interpretation of the safety, tolerability, or efficacy of the study medication.

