6.4 Subject Withdrawal

All subjects have the right to withdraw from this study at any time. In addition, it is the right of the Investigator to remove subjects from the study as a result of adverse reactions, a protocol violation, or non-compliance, or any other reason. Subjects must be discontinued for the following reasons:

- Subject withdraws consent or requests discontinuation from the study for any reason;
- Occurrence of a medical condition or circumstance that exposes the subject to substantial risk and/or does not allow the subject to adhere to the requirements of the protocol as determined by the Investigator;

Protocol: BPN14770-CNS-203 Tetra Discovery Partners, Inc.

Date: 25 June 2018 Confidential

• Any serious adverse event (SAE), clinical significant adverse event, severe laboratory abnormality, concomitant illness, or other medical condition which indicates to the Investigator that continued participation is not in the best interest of the subject;

- Requirement for prohibited concomitant medication;
- Termination of the study by the Sponsor or the regulatory authority.

Should a subject withdraw after administration of BPN14770 (or placebo), or should the Investigator decide to withdraw the subject, all efforts will be made to complete and report the protocol-stipulated observations up to the time of withdrawal. Week 12 procedures (see Section 10.3.5 and Section 16.1 Schedule of Study Assessments) will be completed at the time of the subject's withdrawal and an explanation provided as to why the subject is withdrawing or being withdrawn from the study.

In a case of subjects lost to follow-up, attempts to contact the subject must be made and documented in the subject's medical records.

The Investigator must document the primary reason for discontinuation of a study subject on the appropriate case report form (CRF). If the reason for withdrawal is a clinical AE, monitoring will continue until the AE resolves or the Investigator assesses the AE as chronic and stabilized.

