7.7 Prior and Concomitant Medications

A prior medication is defined as any psychotropic or anti-epileptic medication taken by the subject for more than 28 days during the 6 months prior to first dose of study drug (Day 1), which was subsequently discontinued within that same 6 month period.

A concomitant medication is defined as any medication taken 14 days prior to the first dose of study drug (Day 1) and during the study through the Week 13 Follow-up Visit should be recorded with indication, daily dose, and start and stop dates of administration.

Current treatment with no more than 3 prescribed psychotropic medications is allowed. Anti-epileptic medications are permitted and are not counted as psychotropic medications if they are used for treatment of seizures. Anti-epileptics for other indications, such as the treatment of mood disorders, count towards the limit of three permitted medications. Permitted concomitant psychotropic medications must be at a stable dose and dosing regimen for at least 2 weeks prior to the commencement of study medication.

Anti-epileptic medications must be at a stable dose and dosing regimen for 12 weeks prior to Screening and must remain stable during the period between Screening and the commencement of study medication.

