7.8 Other Therapeutic Treatments

Behavioral and therapy treatments/interventions must be stable for 4 weeks prior to Screening and must remain stable during the period between Screening and the commencement of study medication, and throughout the study.

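### Background psychotropic and anti-epileptic doses must be stable only until first dose, so elective changes during the 24 treatment weeks break no written rule; the likely cost is modest extra noise

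*Protocol*

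**What the plan says.** **Drugs.** Protocol 6.2 item 4 (psychotropics) and item 5 (anti-epileptics) require a stable regimen before Screening, which then "must remain stable during the period between Screening and the commencement of study medication". Nothing is said about the time after first dose. The synopsis matches; its item 4 reads "least 2 weeks prior to Screening and must remain stable during the period between Screening and the commencement of study medication". In section 7.7 the anti-epileptic rule also ends at first dose. The psychotropic rule there asks for stability "for at least 2 weeks prior to the commencement of study medication", a slightly different lead-in from item 4, with the same end point.

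**Behavioural therapy.** Item 7 and section 7.8 go further: such treatment "must remain stable during the period between Screening and the commencement of study medication, and throughout the study".

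**Other medication rules.**
- No more than three psychotropics are allowed. Anti-epileptics given for non-seizure indications "count towards the limit of three permitted medications"; those given for seizures do not count.
- Section 6.4 makes "Requirement for prohibited concomitant medication" a reason for mandatory discontinuation, but no section names a prohibited drug.
- Concomitant medications "should be recorded with indication, daily dose, and start and stop dates of administration", with updates taken at the post-dose calls and visits (10.3.2 to 10.3.7).

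**Analysis.** SAP 4.1 defines the completer set as subjects who finish both periods without significant protocol deviations. SAP 10 lists concomitant medications by subject. The SAP gives no rule for handling changes in them.

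**The concern.** The plan recognises that a changing co-intervention can disturb the comparison, and it controls behavioural therapy for that reason. It leaves out the drugs, although psychotropics may act directly on the irritability, anxiety and hyperactivity that the ABC and ADAMS measure.

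The design makes this relevant. Each subject is his own control across two 12-week periods, both periods are referred to one pre-treatment baseline, and the ABC and ADAMS have one post-dose score per period, at Week 12. A drug change between the two Week 12 scores goes straight into the within-subject difference. It adds noise if it is unrelated to treatment, and bias if it is related.

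The Period 1 ANCOVA is exposed to a different pattern. A change in Period 1 whose effect persists cancels in the crossover but stays in the Period 1 comparison. Neither analysis is a general back-up for the other.

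Because such a change breaks no written rule, it is not a deviation, and the completer analysis, which is the plan's robustness check, would not remove it.

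**Working it through.** **1. Does any other rule close the gap?**
- The three-drug limit, read as ongoing, would stop a fourth psychotropic. It does not reach dose changes, swaps or stops within the limit, or seizure anti-epileptics.
- The withdrawal rule on prohibited medication cannot be applied without a list.
- The investigator's freedom to withdraw a subject (6.4) is discretion, not a rule on drug changes.

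So the gap stands for elective changes of those kinds.

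**2. Reproduce the plan's own figures.** Inputs from Protocol 11.1 and SAP 4.3: SD 3, 5% alpha (taken as two-sided), 30 evaluable subjects, 15 per sequence. I read the SD as within-subject for the crossover and use the noncentral t with 28 df.
- Crossover: SE = 3 × √(2/30) = 0.775. Detectable difference at 80% power is 2.248, against 2.25 stated; power at 2.25 is 80.1%.
- Period 1 only: SE = 3 × √(2/15) = 1.095. Detectable difference is 3.179, against 3.19 stated; power at 3.19 is 80.3%.

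Reading SD 3 as the SD of the within-subject difference gives 1.59 instead of 2.25, so the within-subject reading is the right one.

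**3. Noise unrelated to treatment (the main case).** Assume that a proportion p of subjects shifts by d units in Period 2 only, equally in both sequences. The documents give neither p nor d. The within-subject difference has variance 2 × 3² = 18 without changes and 18 + d² × p × (1 − p) with them. SE = 0.5 × √(2 × variance/15).

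| d | p | Variance | SE | Power at 2.25 |
|---|---|---|---|---|
| 0 | – | 18.00 | 0.775 | 80.1% |
| 1.5 | 0.1 | 18.20 | 0.779 | 79.6% |
| 1.5 | 0.2 | 18.36 | 0.782 | 79.3% |
| 1.5 | 0.3 | 18.47 | 0.785 | 79.0% |
| 3 | 0.1 | 18.81 | 0.792 | 78.3% |
| 3 | 0.2 | 19.44 | 0.805 | 77.0% |
| 3 | 0.3 | 19.89 | 0.814 | 76.0% |

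**4. How bias would enter if changes tracked treatment.** Suppose m of 15 subjects in one sequence improve by d units through a drug change.
- *Period 2 only.* Crossover bias = 0.5 × (m/15) × d = m × d/30. With d = 3 this is 0.10 units for m = 1 and 0.30 units for m = 3, or 4% and 13% of 2.25. On placebo it shrinks the estimate and power becomes 76% or 66%. On active drug it inflates the estimate by the same amount and apparent power becomes 83% or 88%. The Period 1 ANCOVA does not move.
- *Period 1 on placebo, with a constant effect that persists.* Crossover bias is 0. Period 1 bias = m × d/15, which is 0.20 or 0.60 units. Period 1 SE = √((18 + d² × p × (1 − p))/15) with p = m/15, giving 1.112 or 1.138. At the plan's Period 1 effect of 3.19, power falls from 80% to 74% or 59%.

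These bias cases show mechanism only. They put every changer in one sequence, moving in one direction, by 3/2.25 = 133% of the target effect. Nothing in the documents supports those choices. With d = 1, the Period 2 placebo case gives 79% (m = 1) or 76% (m = 3).

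**The case against.** The strongest reply is that the proposed wording does not reach the worst cases. Section 7.4 blinds site staff and subjects, so elective changes have little reason to follow treatment. Changes that would follow it come after worsening, adverse events or response, and most of those would qualify as medically necessary and stay permitted. This stands. It is why the point rests on noise.

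A reader might infer that the gap biases the trial seriously, and cite crossover power of 66%, or Period 1 power of 29% (three changers, 3-unit shift, true effect 2.25). The documents do not support that. Both figures need the unsupported pattern in step 4. The 29% also tests Period 1 at 2.25, where power is only 51% with no drug changes at all; the plan states 3.19 for that analysis.

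A reader might also infer that background drugs are wholly unregulated during treatment. That goes too far, given the three-drug limit.

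Other replies carry some weight:
- The trial is exploratory and studies patients "receiving standard medications". Letting background care vary and analysing everyone as randomised is defensible. It does not explain why therapy is held fixed and drugs are not.
- Eligibility lowers the need for changes: major psychiatric conditions are excluded, and subjects with a seizure history must have been seizure-free.
- NIH-TCB, KiTAP, CGI and VAS are scored at Weeks 6 and 12 and modelled with both visits, so the one-score calculation does not describe them.
- In 30 subjects, individual changes can be read from the listings, so a table alone would add little.

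**Conclusion.** The gap is real and consistent across the synopsis, 6.2 and 7.7. Its demonstrable cost is small: at 2.25 units, crossover power falls from 80.1% to between 76.0% and 79.6%. That range assumes that 10% to 30% of subjects shift by 1.5 to 3 units in Period 2, independently of treatment, with one post-dose score per period and the plan's SD of 3. The rate and size of such shifts are not in the documents.

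Treatment-related bias, in the crossover or in the Period 1 ANCOVA, is possible and could go in either direction. Its size is unknown, and blinding limits it for elective changes. The point is a cheap improvement of minor to moderate severity, justified because the plan already applies the same clause to behavioural therapy.

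**What to change.** **Protocol.** In 6.2 items 4 and 5, section 7.7 and the synopsis, extend the stability requirement with words such as: *and throughout the study (through Period 2 Week 12), unless a change is medically necessary*. Record other changes as protocol deviations. Do not make every change an automatic exclusion from the completer set.

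**SAP, optional.** Specify, before unblinding, a table of psychotropic and anti-epileptic starts, stops and dose changes by treatment and period, to help in reading the results. Any analysis that drops data after a change should be a sensitivity analysis only, with the caveat that the exclusion may be informative.

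**Cost.** Wording in three places and, if wanted, one table. The protocol already collects daily dose and start and stop dates. Background drugs stay allowed, so the study population does not change. The price is slightly less freedom for discretionary changes. Medically necessary changes, and any bias from them, remain, and the clause helps only subjects still on study when it is adopted.
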